14.1 PRIMARY EFFICACY ANALYSIS

14.1.1 Analysis Population and Estimand

The primary endpoints will be analyzed using a “composite strategy” (International Conference on Harmonization (ICH) guideline E9 addendum on estimands and sensitivity analysis in clinical trials to the guideline on statistical principles for clinical trials). The estimand is defined by the following:

- Population: adult recipients of a single pulmonary allograft with clinically defined BOS, matching the inclusion and exclusion protocol criteria.
- Variable: FEV₁ data at Week 48 (visit 9) collected from the on site **CCI** spirometer (data collected with the **CCI** home spirometer will be used for supplementary analyses). Only accepted over-reader best FEV₁ data for the session from **CCI** will be used for analysis; data will not be re-derived.
- Intercurrent events: After IEs such as stopping treatment with L-CsA, augmentation of SoC therapy, etc., FEV1 measurements will still be collected and used in the analysis. In case of IEs preventing the use of FEV1 measurements, i.e. death and re-transplantation, the FEV1 will be imputed as treatment failure: FEV1 equal to zero for all visits subsequent the event. Rejected spirometries are those that did not meet the American Thoracic Society criteria; if rejected, then they would be re-done but there may be cases where they are rejected twice and resulting in missing data. Rejected spirometry is not an indicator of a better/worse outcome and can be assumed to be MAR.

- Population-level summary: difference in mean change from baseline in the FEV₁ at week 48 between treatment groups.

14.1.2 Working Hypothesis

The alternative hypothesis (H_1) for this trial is that L-CsA plus SoC is superior to SoC alone in preserving FEV₁, i.e., under H_1 it is expected that patients treated with L-CsA plus SoC will exhibit a smaller mean FEV₁ decline between baseline and the end of Week 48 than those who receive SoC alone.

Due to the decrease in sample size (see section 8.2) then there will be an underpower to assess the statistical hypothesis, and instead the primary analysis will be descriptive in nature.

14.1.3 Analysis Model

The primary efficacy analysis will be carried out using a LMM for repeated measurements, using all observed available FEV₁ measurements. In case of death or re-transplantation events, FEV₁ will be imputed as zero at each nominal day post event.

The dependent variables are the absolute change from baseline of FEV₁ measurements at visit 2 (i.e., the first post-baseline visit) through visit 9 (Week 48). For the definition of baseline FEV₁ please refer to section 8.1.1.

A flexible and robust model will be chosen for the random part of the LMM according to a pre-specified stepwise procedure (see next section). The original protocol considered the fixed part of the LMM containing the following (except from the intercept): time cubic splines, treatment, the interactions of time splines by treatment, baseline FEV₁, the interactions of time splines with the baseline FEV₁, region (North America versus all other countries together), underlying indication for lung transplant (COPD versus all others), and use of azithromycin at randomization (i.e. Baseline, Visit 1). Due to the reduced sample size (see section 8.2), the covariates will be selected taking into account model convergence (as detailed below).

The primary efficacy parameter will be estimated from the model by the adjusted difference between treatment groups in mean FEV₁ change from baseline after 48 weeks. The p-value for the null hypothesis of no difference and a two-sided 95% confidence interval for the difference will be provided. The comparison between treatment groups at all the other visits (2-8) will also be presented.

A figure of observed mean change from baseline and standard errors at each visit, by treatment group will be presented. A figure with adjusted mean changes from baseline at each visit by treatment group derived from the LMM will be provided.

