Statistical Considerations:	
Due to serious enrolment problems (see Sample size), it is expected to close this study with fewer than 110 patients originally planned and consequently the study will be underpowered for the assumed effect. Therefore, all planned analyses will be performed and the impact of the reduced sample will be considered. For the same reason, the pre-planned blinded interim analysis for sample size re-estimation will not be performed. The Statistical Analysis Plan (SAP) will provide a detailed description of the statistical analyses.
 
FEV1 data collected from the CCI [REDACTED] spirometer will be considered primary, while the data collected with the CCI [REDACTED] home spirometer will be used for supportive analyses.
 
The primary estimand to be assessed will be the between-treatment-group difference in mean absolute change in FEV1 between baseline and the end of Week 48, assessed in the patient population defined by the inclusion and exclusion criteria, regardless of whether or not starting additional immunosuppressive medication or stopping of the investigational treatment had occurred (Treatment Policy Strategy, efficacy). Testing will be performed on the full analysis set (FAS) which will include all randomized patients who have at least one post-baseline assessment of the primary outcome measure.
 
All available FEV1 measurements will be entered into a linear mixed model (LMM), with change in FEV1 between baseline and subsequent visits as the dependent variable, randomized treatment, time, region (North America versus all other countries together), and underlying indication for transplant (COPD versus all others) as the independent factors, and with baseline FEV1 and azithromycin use at randomization as covariates. Moreover, the treatment by time interaction and the baseline FEV1 by time interaction will be included into the model. Due to the reduced sample size, the covariates will be selected taking into account model convergence.
 
Several sensitivity analyses were planned in the original protocol. Due to the reduced sample size, the value of these sensitivity analyses is reduced and some of them might not be applicable.
 
Sensitivity analyses will be performed in the per-protocol analysis set as well as using an alternative estimand according to which outcome measurements will only be used for the period during which patients were on randomized treatment (i. e., prior to the initiation of additional immunosuppressive therapy or L-CsA discontinuation; While-on-Treatment strategy, efficacy). Moreover, sensitivity analyses will also be performed to assess the validity of the Missing-at-Random assumption for the LMM.

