##### *The analysis model*

The primary efficacy analysis will be carried out with a linear mixed model (LMM) for repeated measurements, using all available FEV1 measurements. The dependent variables are the absolute change from baseline of FEV1 measurements at visits 2 (i. e., the first post-baseline visit) to 9 (Week 48).

A flexible and robust model will be chosen for the random part of the LMM according to a pre-specified stepwise procedure as described in detail in the SAP. The fixed part of the LMM is specified as follows. Time will be represented in a flexible and robust way using cubic splines, as

[figure not shown]
described in detail in the SAP. The model proposed in the original protocol contained the following covariates (apart from the intercept): time splines, treatment, the interactions of time splines by treatment, baseline FEV1, the interactions of time splines with the baseline FEV1, region (North America versus all other countries together), underlying indication for lung transplant (COPD vs all other), and use of azithromycin at randomization. Due to the reduced sample size (see [section 15.5 Sample Size Considerations](#)), the covariates will be selected taking into account model convergence. The primary efficacy estimand will be estimated from the model as the adjusted difference between groups in mean FEV1 change from baseline after 48 weeks. The one-sided p-value and the two-sided 95% confidence interval will be provided. Superiority of L-CsA will be demonstrated by a statistically significant result (defined as p<0.025, one-sided) in favor of the L-CsA plus SoC treatment.

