7.2 Randomization and Stratification

At the Baseline visit (V1), after all inclusion and exclusion criteria have been fully evaluated, eligible patients will be randomized with equal probability to one of two treatment arms, a control arm (SoC alone) and an investigational arm (L-CsA plus SoC). The investigational medicinal product (IMP) is L-CsA. To assure balance between treatment arms with regard to key variables and potential confounders, stratification prior to randomization will be performed for the following variables:

- Screening FEV₁ ≥81% of personal best FEV₁ value post-transplant versus Screening FEV₁ between 80-51% of personal best FEV₁ value post-transplant
- Underlying indication for lung transplant: Chronic obstructive pulmonary disease (COPD) versus all other underlying diseases
- Region: North America versus all other countries together

Within each of the 8 strata, patients will be randomly assigned with equal probability (1:1) to either the investigational or control arm using a permuted blocks randomization. The randomization code, including specification of the block size, will be generated by a statistician not otherwise involved with the trial, using validated software. The unique randomization number and treatment assignment of each patient will be provided to the Investigator through the electronic Case Report Form (eCRF) after eligibility has been verified. The number assigned to a patient will be that patient's unique identifier throughout the clinical trial and cannot be re-assigned to another patient.

This is an open-label clinical trial. Clinical trial monitors, treating physicians, study nurses, study coordinators, and enrolled patients will not be blinded to treatment assignment.

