8.1.1 Baseline Definition

CCI [REDACTED] baseline FEV₁: the FEV₁ value that is the mean of the best FEV₁ obtained with the CCI [REDACTED] study spirometer at the Screening Visit and the pre-randomization best FEV₁ obtained at the Baseline Visit (V1) is referred to as “baseline FEV₁”. If the value at Screening visit is missing, then the baseline FEV₁ will be the pre-randomization value from the Baseline Visit (V1). If the pre-randomization value at Baseline Visit (V1) is missing, then the baseline FEV₁ will be the value from the Screening Visit.

Other CCI [REDACTED] baseline spirometry values: will be defined similarly as for Baseline FEV₁.

CCI [REDACTED] baseline FEV₁: will be defined similarly as for CCI [REDACTED] baseline FEV₁ but using the CCI [REDACTED] home spirometer.

L-CsA:
Treatment of BOS after SLT

Protocol Number:
BT – L-CsA – 301 – SLT

Sponsor:
Zambon SpA

Baseline laboratory values: the last measurement obtained prior to or at the Baseline Visit at V1.

Other baseline measurements: unless otherwise specified, baseline refers to measurement obtained at the Baseline Visit at V1.

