14.1.4 Specification of the Model

For valid inference on the primary efficacy parameter, the evolution of FEV_1 in both treatment groups should be modeled as a flexible function in time, without unnecessarily strong assumptions.

Therefore, time will be modeled assuming that the time evolution of FEV_1 is a smooth function of time. Cubic splines will be used with a large enough number of parameters to minimize the risk of misspecification. We will choose one knot at 182 days, i.e., halfway between the first (day 28) and the last scheduled measurement (337 days). So, it is assumed that the mean of FEV_1 is a third-degree polynomial at each of the two intervals, smoothly connected, equal at day 182 with equal first and second derivative. Thus, 4 parameters per group are used to model time. In total, as many as 12 parameters in the model will involve time, ensuring robust estimation of the time evolution of FEV_1 . Denoting the covariates associated with the splines by $S_1=t$, $S_2=t^2$, $S_3=t^3$ and $S_4=\max(t-182,0)^3$, the treatment group by T ($0=SoC$; $1=L-CsA$ plus SoC), the day of the measurement by t and the baseline FEV_1 by X , the fixed part of the model will contain the following covariates:

Intercept, $S_1, \dots, S_4, T, T*S_1, \dots, T*S_4, X, X*S_1, \dots, X*S_4$, other covariates

The Kenward-Roger adjustment will be used for the denominator degrees of freedom needed for hypothesis tests and confidence intervals.

The other covariates are:

- underlying indication for lung transplant (COPD versus all others)
- Region (North America versus all other countries together)
- Use of azithromycin at randomization.

In case of collinearity or non-convergence, covariates will be dropped in the above order, starting with the last. With the final selection of covariates in the model in place, the random part of the LMM will then be selected by comparing the Akaike Information Criterion (AIC) of three models:

- model with random intercept and random time;
- model with random intercept, random time and random squared time;
- model with random intercept, random time, random squared time, and random cubic time.

The model with the lowest AIC will be adopted for the primary analysis.

The core excerpt of **CCI** code for the primary analysis is reported in section 17.1.

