14.2.1 ANCOVA

The population-level summary for the variable will be altered. An analysis of covariance (ANCOVA) model will be performed on the changes from baseline in FEV_1 to Week 48, using the same stratification factors and the same covariates described for the LMM for the primary efficacy analysis (except for time factors). In case of death or re-transplantation events, FEV_1 will be imputed as zero at each nominal day post event.

In case of violation of the normality assumption even after log transformation (section 14), then rank transformation will be applied to normalize the data. The same ANCOVA model will be applied to the rank-transformed data.

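### The primary mixed model leaves out one of the three randomization stratification factors (Screening FEV1 as % of personal best), at a small cost in precision and with no bias

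*SAP*

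**What the plan says.** SAP 7.2 gives the purpose of stratification as "To assure balance between treatment arms with regard to key variables and potential confounders". The first factor is "Screening FEV₁ ≥81% of personal best FEV₁ value post-transplant versus Screening FEV₁ between 80-51% of personal best FEV₁ value post-transplant"; the others are COPD versus other indication, and region. Patients are randomized in permuted blocks within the resulting 8 strata. Protocol 9.3 lists the same three factors.

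The fixed part of the primary model (SAP 14.1.3) contains cubic time splines, treatment, treatment by time, baseline FEV1, baseline FEV1 by time, and "region (North America versus all other countries together), underlying indication for lung transplant (COPD versus all others), and use of azithromycin at randomization". SAP 14.1.4 repeats these three further covariates and drops them from the end of its list on collinearity or non-convergence, so azithromycin goes first. The protocol synopsis has "region (North America versus all other countries together), and underlying indication for transplant (COPD versus all others) as the independent factors", with baseline FEV1 and azithromycin as covariates. Protocol 15.2.3.1 ends its list with "underlying indication for lung transplant (COPD vs all other), and use of azithromycin at randomization". None of the four lists includes the Screening FEV1 stratum.

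Baseline FEV1 (SAP 8.1.1) is an absolute value, the mean of the best Screening and pre-randomization Visit 1 readings. The supplementary ANCOVA (SAP 14.2.1) is to be fitted "using the same stratification factors and the same covariates described for the LMM".

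For the random part, SAP 14.1.4 adopts whichever of three structures has the lowest AIC. SAP 14.1.5 specifies four random effects per patient, reduced only on non-convergence or a covariance matrix that is not positive definite.

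**The concern.** An analysis normally carries the factors used to stratify randomization. Balancing on a prognostic factor reduces the true variability of the treatment estimate; if the model omits the factor, the reported standard error does not reflect that reduction. Here the plan adjusts for azithromycin, which was not a stratification factor, and omits one that was.

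Absolute baseline FEV1 is not a full substitute. Two patients with the same volume can be in different strata because their personal bests differ. Under inclusion criterion 2b (protocol 10.1), patients above 85% of personal best enter only with a recent loss of at least 200 mL or a history of BOS progression, so the stratum may also carry information about recent decline. SAP 14.5 itself uses % of personal best to define disease severity.

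What is at stake is the width of the 95% interval and the size of the p-value that SAP 14.1.3 reports. With 62 patients (SAP 8.2), that interval is the main efficacy result. The ANCOVA wording adds an ambiguity: the LMM sections label nothing as a stratification factor and list two of the three, so two programmers could fit different models.

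**Working it through.** **1. The plan's own figure.** For 200 mL, SD 350 mL and one-sided alpha 0.025, an exact t-test needs 49.05 per arm for 80% power, so 50; power at 50 per arm is 80.8%. The stated size reproduces. It rests on an unadjusted test, so it does not depend on the omitted factor. At 31 per arm (62 patients) power is 60.0% before dropout.

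**2. Factor count.** Stratified by: Screening FEV1 stratum, indication, region. In the LMM: indication, region. Omitted: one of three.

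**3. Direction.** Week-48 ANCOVA simulations (N = 62, 8 strata; assumed blocks of 4 and prevalences 35%, 40%, 50%; no zero-imputed values) gave these one-sided type I errors without and with the stratum, by assumed share of variance explained:

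| Share | Without | With |
|---|---|---|
| 0 | 0.024 | 0.025 |
| 0.05 | 0.021 | 0.023 |
| 0.10 | 0.019 | 0.023 |
| 0.20 | 0.017 | 0.027 |

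The reported SE is too large rather than too small: at 0.10, without the stratum, the mean reported SE was 89.6 mL against a true sampling SD of 84.4 mL.

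**4. Size with no zero-imputed values.** Let R² be the stratum's share of Week-48 variance (assumed 0.03-0.15) and q the share of the stratum that baseline FEV1 captures. In simulation q was 0.16 to 0.32, for an assumed coefficient of variation of personal best of 35% to 20%. The SE ratio, without over with, is about √[1 + R²(1 − q)/(1 − R²)].

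- R² = 0.03: √(1 + 0.0204/0.97) = 1.010 to √(1 + 0.0252/0.97) = 1.013.
- R² = 0.15: √(1 + 0.102/0.85) = 1.058 to √(1 + 0.126/0.85) = 1.072.

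Estimating the extra term costs 0.2-0.3%. Simulation gives roughly 1% and 6.5%. On a simple scale, 350 × √(2/31) = 88.9 mL and 1.96 × 88.9 = 174 mL. Dividing by 1.01 or 1.065 narrows the half-width by about 2 or 11 mL.

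**5. Size with zero imputation.** SAP 14.1.3 sets FEV1 to zero after death or re-transplantation. Assume 5% of patients, independent of stratum, and mean baseline FEV1 of 1.2-1.8 L. The added variance is about 0.05 × 0.95 × 1200² = 68,400 mL² to 0.05 × 0.95 × 1800² = 153,900 mL², on top of 0.95 × 350² = 116,375 mL². The stratum's variance is 0.95² × R² × 122,500: 3,317 mL² at 3% and 16,583 mL² at 15%.

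- 3%: the share falls to 3,317/184,775 = 1.8% or 3,317/270,275 = 1.2%. The step 4 formula gives ratios of 1.004-1.008.
- 15%: the share falls to 9.0% or 6.1%. Ratios are 1.022-1.041.

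Simulation, which includes the cost of the extra term, gives 0.2-0.5% and 2.5-3.6%.

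**6. In the LMM itself.** REML simulations of the 14.1.4 fixed part (400 trials per setting, 10% dropout, assumed stratum prevalence 45% and variance split, no zero imputation) show what a main effect recovers. If the stratum is a constant shift, the gain is 1.1-1.4% (3%) and 6.0-7.5% (15%). If it acts on the rate of decline, the gain is about 0.2% and 0.9-1.1%.

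**7. Random-part rules.** In simulation the two rules chose different structures in 36-74% of trials, with Week-48 estimates then differing by a median of 1.0-4.1 mL. With 5% zero imputation the figures were 44-87% and 2.2-4.5 mL. The frequencies depend on the threshold used for positive definite.

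**The case against.** The case for leaving the model alone is substantial. All analyses are declared descriptive (SAP 14, 14.1.2), so no formal decision depends on the width of the interval. Randomization already balances the stratum, baseline FEV1 enters with four time interactions, SAP 14.5 compares FEV1 change within % of personal-best categories, and SAP 10 tabulates the stratification factors. SAP 14 warns of non-convergence, and every patient in this open-label trial has been randomized. The 3-15% share has no source in the documents. Prevalence, block size and variance split are assumed too, and protocol 9.3 deliberately withholds the block size.

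Most of this stands and limits the point to minor. It does not remove it: a p-value and interval are still reported, the factor is already collected, and subgroup tables do not adjust the primary estimate.

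A reader might infer that a stratum-by-time interaction is required because it would recover more under a rate effect. The documents do not support requiring it: neither of the other stratification factors receives one, although protocol 9.3 says COPD affects FEV1 slopes. On the ANCOVA, the phrase can fairly be read as the LMM's two factors; the criticism is only that it is not explicit. On the random part, 14.1.5 can be read as a fallback to 14.1.4, but it does not say so. The model code in SAP 17.1 is redacted and is not counted as missing.

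**Conclusion.** The omission is plain in the text and unexplained in any legible section. Its consequence is a Week-48 interval and p-value that can be slightly conservative. Under the assumed 3-15% share, the ANCOVA standard error without the stratum is roughly 1-6.5% larger with no zero-imputed events and roughly 0.2-3.6% larger with 5% of patients so imputed. In the LMM a main effect recovers less than this if the stratum acts on the rate of decline.

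Three stronger conclusions might be drawn and are not supported. The estimate is not biased, because the factor is balanced by design. Type I error is not inflated; in step 3 the test without the stratum stayed below 0.025. Nor is there a protocol-SAP conflict, since both documents carry the same covariate list.

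The ANCOVA wording and the two random-part rules are secondary, with numerical effects that are small against the 200 mL used for planning. Overall importance: minor.

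**What to change.** - **SAP 14.1.3-14.1.4:** add the Screening FEV1 stratum, as randomized, as a main effect beside indication and region. Place it with those two, ahead of azithromycin in the list, so that azithromycin is still dropped first. A stratum-by-time term is optional.
- **If the primary model is not to be changed after all 62 patients were randomized:** pre-specify the same model as a sensitivity analysis.
- **SAP 14.2.1:** name all three stratification factors.
- **SAP 14.1.4 and 14.1.5:** state that the lowest AIC governs among candidates that converge with a positive-definite covariance matrix.

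The cost is one degree of freedom and a slightly larger model where convergence is already a worry. If the stratum explains nothing, the SE is about 0.2-0.3% wider. SAP 5 requires timing and rationale to be documented. No new data are needed.

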14.1.4 Specification of the Model

For valid inference on the primary efficacy parameter, the evolution of FEV_1 in both treatment groups should be modeled as a flexible function in time, without unnecessarily strong assumptions.

Therefore, time will be modeled assuming that the time evolution of FEV_1 is a smooth function of time. Cubic splines will be used with a large enough number of parameters to minimize the risk of misspecification. We will choose one knot at 182 days, i.e., halfway between the first (day 28) and the last scheduled measurement (337 days). So, it is assumed that the mean of FEV_1 is a third-degree polynomial at each of the two intervals, smoothly connected, equal at day 182 with equal first and second derivative. Thus, 4 parameters per group are used to model time. In total, as many as 12 parameters in the model will involve time, ensuring robust estimation of the time evolution of FEV_1 . Denoting the covariates associated with the splines by $S_1=t$, $S_2=t^2$, $S_3=t^3$ and $S_4=\max(t-182,0)^3$, the treatment group by T ($0=SoC$; $1=L-CsA$ plus SoC), the day of the measurement by t and the baseline FEV_1 by X , the fixed part of the model will contain the following covariates:

Intercept, $S_1, \dots, S_4, T, T*S_1, \dots, T*S_4, X, X*S_1, \dots, X*S_4$, other covariates

The Kenward-Roger adjustment will be used for the denominator degrees of freedom needed for hypothesis tests and confidence intervals.

The other covariates are:

- underlying indication for lung transplant (COPD versus all others)
- Region (North America versus all other countries together)
- Use of azithromycin at randomization.

In case of collinearity or non-convergence, covariates will be dropped in the above order, starting with the last. With the final selection of covariates in the model in place, the random part of the LMM will then be selected by comparing the Akaike Information Criterion (AIC) of three models:

- model with random intercept and random time;
- model with random intercept, random time and random squared time;
- model with random intercept, random time, random squared time, and random cubic time.

The model with the lowest AIC will be adopted for the primary analysis.

The core excerpt of **CCI** code for the primary analysis is reported in section 17.1.

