14 EFFICACY

For each efficacy analysis, the adequacy of the model assumptions will be checked, and if it is found that these are inadequate then alternative approaches may be performed.

For all variables assumed to be normally distributed, the conditional studentized residuals from this model will be tested using the Shapiro-Wilk test. If the assumption of normality of these residuals is violated, then a log-transformed model will be fitted. The need for a possible log transformation of these variables will be investigated prior to unblinding by assessing the model

residuals without a treatment term. Where data are transformed for analysis, back transformation will be applied for the presentation of results. Presentation of the tables will be amended as needed for this, with the addition of an explanatory footnote.

Classification and imputation of missing data will be completed prior to any transformation of the data for analysis.

As a general remark for all efficacy endpoints based on spirometry data, values collected at 1h and 4h post dose will not be used for any efficacy analyses as they are collected only for safety evaluations.

It is important to note that due to the decrease in sample size (see section 8.2) the study will be underpowered for the assumed effect to assess the statistical hypothesis for the primary endpoint. The statistical modelling for the primary endpoint for the pre-specified covariates may lead to non-convergence of the models and selective covariates will have to be considered. Supplementary analyses for the primary endpoint, **CCI** will adopt simple statistical analyses. As a result, all analysis for this study will be descriptive in nature.

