14.1.5 Specification of the Covariance Model

The model for the mean uses the actual times of the visits as a continuous variable instead of the scheduled visit times. Therefore, the covariance model will also use the actual visit times, using random effects. For valid inference, the model for the covariance should be correctly specified.

Thus, the preference will be for models with relatively many parameters in order to ensure robust estimation of the covariance, though this may lead to a loss of efficiency.

Therefore a model will be specified with four per patient random effects: intercept, t , t^2 , t^3 , with an unstructured covariance matrix. This covariance model contains 11 parameters, ensuring sufficient robustness. In case the model does not converge, or the covariance matrix is not positive definite, we will drop terms from the highest order random effect.

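### On collinearity or non-convergence the primary model sheds its covariates, including both stratification factors in it, before its random part is simplified, although the listed covariates are an unlikely cause

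*SAP*

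**What the plan says.** SAP 14.1.4 builds the fixed part from t, t², t³ and max(t−182, 0)³, where t is defined in days ("the day of the measurement by t and the baseline FEV_1 by X"). These four terms are crossed with treatment and with baseline FEV1: "In total, as many as 12 parameters in the model will involve time". No centring or scaling of time or baseline FEV1 is stated. The remaining covariates are listed in the order indication, region, azithromycin.

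The first remedy is in the same section: "In case of collinearity or non-convergence, covariates will be dropped in the above order, starting with the last". Once the covariates are settled, the random part is chosen by AIC among three structures: intercept and t; those plus t²; those plus t³.

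SAP 14.1.5 describes the random part differently: "a model will be specified with four per patient random effects", with an unstructured covariance matrix. It gives a second remedy. If the model does not converge, or the covariance matrix is not positive definite, the highest-order random effect is dropped first.

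SAP 7.2 stratifies randomization by screening FEV1 as a percentage of personal best, by indication, and by region. The first of these is not in the model, which has baseline FEV1 in its place. SAP 14 treats convergence trouble as a real prospect: the pre-specified covariates "may lead to non-convergence of the models and selective covariates will have to be considered".

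**The concern.** The rule acts on terms that are unlikely to cause the trouble. Three binary patient-level covariates have little overlap with a spline in time. A Gaussian mixed model usually fails to converge in its variance parameters, and here there are up to 11 of them for 62 patients. If the rule fires, the analysis can lose azithromycin, then region, then indication, with the cause still in place. The full sequence leaves none of the three stratification factors in the model.

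The order of the two remedies also matters, because non-convergence triggers both. Suppose the model with cubic random effects fails. Under 14.1.4 azithromycin goes first. Under 14.1.5 the random t³ term goes and every covariate stays. The SAP does not say which rule applies, or which random structure is used to judge convergence during the covariate step.

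The consequence reaches past one table. The per-protocol, home-spirometer and COVID-19 analyses (SAP 14.2.3 to 14.2.5) reuse this model. SAP 14 requires the log-transformation question to be examined before unblinding and without a treatment term. It states no such safeguard for dropping covariates.

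**Working it through.** **The SAP's own counts reproduce.**
- Time parameters: 4 (spline) + 4 (by treatment) + 4 (by baseline FEV1) = 12, as stated.
- Covariance parameters: 4×5/2 + 1 residual = 11, as stated.
- Knot: (28 + 337)/2 = 182.5, stated as 182.
- All fixed columns: 1 + 4 + 1 + 4 + 1 + 4 + 3 = 18.
- Records: at most 62 × 8 = 496.

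**Inputs for the design check.** From the documents: 62 patients (SAP 8.2), post-baseline visits at weeks 4, 8, 12, 16, 24, 32, 40 and 48 with the protocol's windows (±7 days to week 16, ±14 days after), and the 14.1.4 basis. Assumed, because the documents do not give them: baseline FEV1 mean 1.5 L (SD 0.5), COPD 40%, North America 50%, azithromycin 70%, all independent. Results are medians of 20 draws. The variance inflation factor (VIF) of a column is its total sum of squares about its mean divided by its residual sum of squares on all other columns.

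| Time variable | Covariates kept | Condition number of X | After column scaling | VIF of t² |
|---|---|---|---|---|
| raw days | 3 | 8.33e8 | 2.09e3 | 59,926 |
| raw days | 0 | 8.32e8 | 2.01e3 | 59,899 |
| days/365.25 | 3 | 5.40e3 | 2.09e3 | 59,926 |
| (t−182)/168 | 3 | 4.92e2 | 2.36e2 | 523 |
| (t−182)/168, baseline FEV1 centred | 3 | 1.95e2 | 78.8 | 84 |

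VIFs of indication, region and azithromycin were 1.08, 1.05 and 1.06 in every row that keeps all three. A separate rebuild with other draws gave 8.66e8 with the covariates and 8.64e8 without, and covariate VIFs of 1.01 to 1.06.

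**What the table shows.**
1. Dropping the three covariates leaves conditioning and the time-term VIFs essentially unchanged.
2. Dividing t by a constant multiplies each column by a constant. This helps the raw condition number but cannot change a VIF, since the R² of one column on the others is unaffected. Days/336 behaves the same way (VIF of t² 66,788 in raw days and in t/336 in the separate rebuild).
3. Centring time cuts the VIF of t² from 59,926 to 523. Centring baseline FEV1 as well cuts it to 84.

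**Convergence.** REML fits to 12 simulated trials per setting, with assumed variances, 10% missing visits and one Python optimiser. Entries are clean convergences.

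| Random effects | Raw days, 3 covariates | Raw days, 0 covariates | Centred and scaled, 3 | Centred and scaled, 0 |
|---|---|---|---|---|
| intercept, t, t², t³ | 0/12 | 0/12 | 12/12 | 11/12 |
| intercept, t | 4/12 | 2/12 | 12/12 | 12/12 |

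Removing covariates did not help in either row.

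**Same model.** The columns 1, t, t², t³ and max(t−182, 0)³ span the same space after t is replaced by (t−182)/168. The baseline products likewise span the same space after baseline FEV1 is centred, because all lower-order terms are present. With an unstructured covariance the random part is also only reparameterised. The Week-48 treatment difference is unchanged.

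**The case against.** Four points weigh on the other side.

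- **A remedy for the random part already exists.** This stands. A reader of 14.1.4 alone might infer that dropping covariates is the SAP's only response, but 14.1.5 reduces the random effects. What remains is the order of the two rules and how the step-down from cubic fits with the AIC comparison.
- **Raw days need not make the model fail.** A reader might infer from a condition number of 8.33e8, or about 6.9e17 for X'X, that the model cannot be fitted as written. The documents do not support that. After column scaling the figure is about 2e3, so the fixed part is estimable. Solving the raw-day normal equations directly gave fitted values within 2e-12 of the t/336 fit. A REML routine that scales internally converged in 4 of 4 raw-day data sets with four random effects, to the same likelihood as t/336. The trial's software name (SAP 8.1) and code (SAP 17.1) are redacted, and the code may already rescale time. The convergence counts above illustrate one optimiser and do not predict the trial's behaviour.
- **Dropping a covariate can sometimes be right.** This also stands. The joint distribution of region, indication and azithromycin in the 62 patients is not given. If one were nearly determined by the others, dropping it would cure that collinearity.
- **The consequence is conditional.** Covariates go one at a time, and only on failure. Azithromycin is not a stratification factor, and it goes first. The analysis is declared descriptive, protocol 15.2.3.1 allows covariates to be selected for convergence, and SAP 14.2.1 plans an ANCOVA with the stratification factors and no time terms. This limits the harm. But SAP 14.1.3 still reports an adjusted difference, a p-value and a 95% confidence interval, and the ANCOVA takes its covariates from this model.

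**Conclusion.** The point holds as a mismatch between remedy and likely cause, and as an unreconciled order of two rules. Under the assumed covariate distributions, the terms that 14.1.4 drops have VIFs of about 1.0 to 1.1, and removing them leaves the condition number at 8.3e8 (8.7e8 in the separate rebuild). The full sequence would remove both stratification factors that are in the model. The collinearity is in the uncentred time terms and their products with baseline FEV1.

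The evidence does not show that the primary analysis will fail, that dropping a covariate can never help, or that dividing days by 336 removes the collinearity. The effect of losing the covariates on the Week-48 estimate and its standard error was not computed. The change is justified because it is almost free, makes the analysis reproducible from the text, and keeps the stratified adjustment from depending on a numerical event.

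**What to change.** In SAP 14.1.4 and 14.1.5:

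1. State that on non-convergence, or a covariance matrix that is not positive definite, the random part is simplified first. Say how this fits with the AIC selection, for example that AIC compares only those of the three structures that converge with the full fixed part.
2. Keep region and indication in the fixed part. Drop azithromycin, or another covariate, only if that covariate is itself aliased with the others.
3. State that time is centred and scaled, for example (t−182)/168, in both the fixed and random parts, and that baseline FEV1 is centred wherever it enters. Evaluate the treatment difference at the transformed value of Week 48. If the code already does this, the text should say so.

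The cost is a derived time variable, a centred baseline and a few sentences. Model, estimand and the estimates from a properly converged fit do not change.
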